11.1. DERIVATIONS

- $BMI (kg/m^2) = 10000 * weight (kg) / height (cm)^2$
- Z-score of weight, height, BMI and head circumference will be calculated based on the method described in Section 19.6.1.

Document:	\\quintiles.net\Enterprise\Apps\sasdata\SASa\sas\Shire\Teduglutide\Biostatistics\Documentation\SAP\TE D-C14-006_SAP_Final_V1.0_20170714		
Author:	PPD	Version Number:	Final V1.0
		Version Date:	14Jul2017

Template No: CS_TP_BS016 – Revision 3
Effective Date: 01May2012

Reference: CS_WI_BS005

Copyright © 2012 Quintiles Transnational Corp. All rights reserved.

The contents of this document are confidential and proprietary to Quintiles Transnational Corp. Unauthorized use, disclosure or reproduction is strictly prohibited.

12. MEDICAL HISTORY

Medical history will be presented for the ITT Analysis Set.

12.1. SHORT BOWEL SYNDROME HISTORY

The following Short Bowel Syndrome (SBS) History will be collected at screening and will be summarized and listed:

- Primary reason for the diagnosis of SBS
- Presence of stoma; if Y, stoma type
- Presence any remaining colon; if Y, estimated percent colon remaining and whether the colon is in continuity with the small bowel
- Presence of distal/terminal ileum and ileocecal valve

12.2. GASTROINTESTINAL SYMPTOMS HISTORY

The following Gastrointestinal Symptoms History collected at Baseline will be summarized based on categories of not present, mild, moderate, and severe, with clinical significance also summarized where the event is present:

- Abdominal/belly pain
- Nausea/feeling queasy
- Vomiting/throw up
- Heartburn/reflux/spit up
- Gas/bloating
- Diarrhea/loose stool
- Constipation/very hard stool

A listing will also be presented by treatment group and subject identifier.

12.3. SURGICAL AND MEDICAL HISTORY

Medical and Surgical History will be coded using *Medical Dictionary for Regulatory Activities (MedDRA) version 19.1*. Medical and Surgical History conditions are defined as those

Document:	\\quintiles.net\Enterprise\Apps\sasdata\SASa\sas\Shire\Teduglutide\Biostatistics\Documentation\SAP\TE D-C14-006_SAP_Final_V1.0_20170714		
Author:	PPD	Version Number:	Final V1.0
		Version Date:	14Jul2017

Template No: CS_TP_BS016 – Revision 3
Effective Date: 01May2012

Reference: CS_WI_BS005

Copyright © 2012 Quintiles Transnational Corp. All rights reserved.

The contents of this document are confidential and proprietary to Quintiles Transnational Corp. Unauthorized use, disclosure or reproduction is strictly prohibited.

conditions which began prior to informed consent. Medical and surgical history includes all relevant past medical diagnoses and surgeries other than related to the cause or diagnosis of SBS. Data captured on the Medical and Surgical History page of the CRF will be presented by System Organ Class (SOC) and Preferred Term (PT). SOC will be sorted alphabetically and PT within SOC will be sorted by descending incidence in the Total Teduglutide treatment group.

13. PRIOR AND CONCOMITANT MEDICATIONS

Medications will be presented for the SAF analysis set.

'Prior' medications are those taken by the subject within 14 days before screening and discontinued prior to the first dose of study drug (or the baseline visit for the standard of care treatment arm).

'Concomitant' medications are defined as:

- medications with onset dates on or after the first dose of study drug (or baseline visit for standard of care treatment arm); or
- medications with onset dates prior to first dose of study drug (or baseline visit for standard of care treatment arm) without a stop date or stop date after the first dose of study drug

The subject's usage of prior medication will be assessed at screening and baseline and the subject's usage of concomitant medication will be assessed at the baseline visit and visit thereafter. The changes in medication or dosage of medications will be recorded on the eCRF. Concomitant medications include IV medications mixed into the PN/IV fluids, like heparin or H2 blockers. Medications used for line maintenance, such as TPA, and ethanol and tauridine locks, are also included as concomitant medications. However, IV fluid and nutritional components of parenteral nutrition, including electrolytes, vitamins and minerals, other micronutrients, amino acids, glucose, and lipids, are part of PN/IV will not be included as a prior or concomitant medications.

Medications will be coded to preferred name using *WHO Drug Dictionary (WHODD), 01SEP2016*. Prior and concomitant medication use will be summarized by preferred name using the number and percentage of subjects by treatment group. Medications will be sorted alphabetically by preferred name. Subjects with multiple occurrences of a medication in preferred name will only be counted once within each preferred name. Medication summaries will be presented by treatment group for the SAF analysis set.

A listing of all medications, both prior and concomitant will be presented. The listing will be sorted by treatment group and subject identifier and will include reported name, dose, route of administration, dosing frequency, start date, end date, indication and period of medication

Document:	\\quintiles.net\Enterprise\Apps\sasdata\SASa\sas\Shire\Teduglutide\Biostatistics\Documentation\SAP\TE D-C14-006_SAP_Final_V1.0_20170714		
Author:	PPD	Version Number:	Final V1.0
		Version Date:	14Jul2017
Template No:	CS_TP_BS016 – Revision 3	Reference:	CS_WI_BS005
Effective Date:	01May2012		

(prior only, concomitant only, prior and concomitant). Investigator verbatim as well as coded terms will be included in the listings.

See [Appendix 2](#) for handling of partial dates for medications.

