5.3.4 Prior and Concomitant Medications

The administration of all medications including prior and concomitant medications must be recorded in the appropriate sections of the eCRF.

Prior medications are those taken by the subject within 14 days before the first dose of study drug and discontinued prior to first dose of study drug.

Concomitant medications are those taken by the subject anytime during the treatment period, after the first dose of study drug.

In general, no new medications should be started during the screening period or throughout the 24-week treatment period, unless medically necessary and prescribed by the investigator or by another qualified physician involved in the subject's clinical care and who is aware of the subject's study participation.

The mechanism of action of teduglutide may increase absorption of drugs (eg, motility medication including narcotics and opioids used for the management of SBS, Coumadin, psychotropics, metronidazole, digoxin), so consideration should be given to modifying concomitant medication regimens. Down-titration of concomitant medications should be considered when drugs, especially those with a narrow therapeutic range, are given at dosages that are higher than usual.

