8.1 Demographic and Baseline Variables

Demographic and/or other Baseline variables obtained at the screening and baseline visit are listed below. Abnormal findings of clinical significance (if any) will be recorded as past medical history.

- Demography (including age, sex, and race)
- Medical history
- SBS history, including remnant anatomy
- Vital signs, including temperature, heart rate, blood pressure, body weight, head circumference (up to 36 months of age), height or length, and trends on growth charts
- Physical examination
- Prior medications (medications used within 14 days prior to screening and discontinued prior to first dose of study drug), including drug name, dose, route, reason for use, and therapy dates. Medications used during the treatment period (after the first dose of study drug) will be recorded as concomitant medications.
- Electrocardiogram (12-lead) variables will include general findings of (normal/abnormal/abnormal, clinically significant). The cause of any clinically significant ECG will be specified.
- Laboratory test results: Serum chemistries, hematology, and urinalysis
- Citrulline levels
- Presence of antibodies to teduglutide and titer level, if present (active treatment groups only)
- Gastrointestinal imaging (UGI/SBFT, abdominal ultrasound, colonoscopy/sigmoidoscopy, fecal occult blood) (active treatment groups only)
- Pregnancy testing for females of child-bearing potential (active treatment groups only)
- Nutritional support (eg, PN/IV volume and calorie usage)
- Data entered in the nutritional diaries

Descriptive statistics (mean, median, standard deviation, minimum and maximum values, and the number and percentage of subjects in specified categories by treatment group) will be presented, as appropriate, to summarize the demographic and baseline variables.

Prior and concomitant medications will be coded using the current version of the World Health Organization Drug Dictionary with regard to drug class and drug name. The number and percentage of subjects with specific prior medications will be summarized by treatment group.

Medical history (including surgical history) will be coded using the current version of the Medical Dictionary for Regulatory Activities (MedDRA). The number and percentage of subjects with specific histories will be summarized by system organ class and preferred term for each treatment group.

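### SAP section 13 leaves medicines confined to screening, or stopped on the first-dose day, in neither medication table, and does not separate follow-up starts from on-treatment use

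*SAP*

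**What the plan says.** **Prior use.** SAP section 13: prior "medications are those taken by the subject within 14 days before screening and discontinued prior to the first dose of study drug". For standard of care, the baseline visit replaces first dose. Protocol 8.1 has the same window: "medications used within 14 days prior to screening and discontinued prior to first dose of study drug". Protocol 5.3.4 uses a different anchor: "Prior medications are those taken by the subject within 14 days before the first dose of study drug and discontinued prior to first dose".

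**Concomitant use.** SAP section 13 has two routes. The first is "medications with onset dates on or after the first dose of study drug". The second is an earlier onset "without a stop date or stop date after the first dose of study drug". Neither has an upper time limit. Protocol 5.3.4 does: "Concomitant medications are those taken by the subject anytime during the treatment period, after the first dose of study drug". Protocol 8.1 also ties concomitant use to the treatment period.

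**Collection and listing.** SAP section 13 states that the subject's "usage of prior medication will be assessed at screening and baseline". It also promises: "A listing of all medications, both prior and concomitant will be presented". Each listed record is to be labelled prior only, concomitant only, or both. Protocol 6.1.11 and Table 6-2 collect concomitant medication through Weeks 25-27 and Week 28.

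**Versions.** SAP section 4.3 declares no change of analysis from the protocol. SAP section 2 says the SAP is based on protocol amendment 4. The protocol supplied is at amendment 2.

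**The concern.** A prior/concomitant scheme should give every relevant record exactly one place. This one has a hole at screening and no boundary at the end of treatment.

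Medicines confined to screening are foreseeable. Exclusion criterion 18 tolerates uncomplicated treatment of bacteremia during screening, and inclusion criterion 5 tolerates transient instability such as treatment for sepsis. Protocol 5.3.4 asks that new medicines in screening be started only if medically necessary, so the records that lose their category point to children who had an intercurrent problem shortly before treatment.

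At the other end, a reader of the concomitant table could not tell whether a medicine was needed while the child was on teduglutide or only after it was withdrawn.

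**Working it through.** No figure in the plan needs reproducing. The check applies the definitions as date rules, with day 0 as first dose and Visit 1 at day -S. Protocol 3.2 sets S at a minimum of 14 days and aims for no more than 28. I take screening in SAP section 13 to mean the screening visit.

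**Step 1: classify typical records.**

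| Medicine | SAP section 13 | Protocol 5.3.4 |
|---|---|---|
| In use before Visit 1, stopped on day -5 | prior | prior |
| Stopped 10 days before Visit 1 | prior | neither |
| Started day -10, stopped day -5 | neither | prior |
| Started and stopped in screening, before day -14 | neither | neither |
| Begun before screening, stopped on day 0 | neither | neither |
| First started in Weeks 25-28 | concomitant | not concomitant |

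The day-0 stop fails both SAP rules because its date is neither before nor after first dose.

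**Step 2: size of the screening gap.** There are n = S - 1 days strictly between Visit 1 and first dose, so n(n+1)/2 possible start/stop pairs lie inside screening. Under the SAP all of them are unclassified. Under 5.3.4 the unclassified pairs are those ending before day -14. For S above 14 these span m = S - 15 days, giving m(m+1)/2 pairs.

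- S = 14: 13 × 14/2 = 91 pairs. SAP unclassified 91; 5.3.4 unclassified 0.
- S = 21: 20 × 21/2 = 210 pairs. SAP unclassified 210; 5.3.4 unclassified 6 × 7/2 = 21, leaving 189 prior.
- S = 28: 27 × 28/2 = 378 pairs. SAP unclassified 378; 5.3.4 unclassified 13 × 14/2 = 91, leaving 287 prior.

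These count date combinations and are not patient frequencies. They show that the SAP gap is complete at every screening length, and that 5.3.4 is complete only at the minimum length.

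**Step 3: partial dates.** SAP Appendix 2 imputes a partial medication start in the consent month as the consent date when that month precedes the first-dose month. Consent is scheduled at screening. A medicine truly begun before Visit 1 can therefore be moved into screening and, if stopped before first dose, lose its prior label.

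**Step 4: the open end.** Treatment ends at day 168 and the study at day 196. Follow-up is 196 - 168 = 28 days, and 28/196 = 14.3%. Any medicine first started then is concomitant under the SAP, although no study drug is given. SAP Appendix 2 already defines a reference end date (last dose, or last visit in the treatment period for standard of care), but the section 13 definition does not use it.

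**Step 5: the combined label.** Prior requires a stop before first dose. Concomitant requires an onset on or after it, no stop date, or a stop after it. No single record can satisfy both, so the combined listing label is empty.

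**The case against.** The case on the other side is substantial and limits the point in five ways.

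- **Departure from the protocol.** A reader might infer that the SAP departs from the protocol on prior use. It does not: protocol 8.1 has the SAP's window, and the conflict is between 8.1 and 5.3.4. The governing amendment 4 text is not available, so neither section can be checked in that version.
- **Disjoint windows.** A reader might infer that with 14-day screening the two prior windows never meet, so all screening use is lost. That ignores medicines in use before Visit 1 and stopped in screening. They are prior under the SAP, and also under 5.3.4 if used in its last 14 days.
- **Lost data.** A reader might infer that records disappear. They are lost from the summary tables only. The listing of all medications should still carry them with dates and indication, but no valid period label.
- **Disturbed PN/IV baseline.** A reader might infer that the gap harms the efficacy baseline. The 14-day baseline window in SAP 17.1.1 applies to diary data and equals the whole of screening only when screening lasts exactly 14 days. Prescribed volume uses the most recent prescription. Medication category enters neither formula.
- **Collection after Week 24.** A reader might infer that gathering concomitant medication in follow-up is itself an error. Table 6-2 and 6.1.11 plan it under that label. What is missing is the split, since 5.3.4 and 8.1 both define concomitant use by the treatment period.

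It is also fair to say that start dates in the listing would let a reader separate follow-up medicines by hand. That does not repair the tables.

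**Conclusion.** The concern holds as a drafting fault in the medication definitions. It has four parts: no category in SAP section 13 for medicines confined to screening or stopped on the first-dose day; conflicting prior windows in protocol 5.3.4 and 8.1, of which 5.3.4 has its own gap once screening exceeds 14 days; no split between treatment and follow-up; and one listing label that cannot be used.

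The consequence is minor. It affects descriptive tables in a study without hypothesis testing. The number of children affected cannot be estimated from the documents.

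The conclusion rests on a literal, date-level reading and on screening meaning the screening visit. The SAP's internal gap does not depend on the protocol version; the comparison with 5.3.4 and 8.1 does, and holds for the supplied amendment 2 text only.

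**What to change.** In SAP section 13:

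- Define prior as any medicine taken at any time from 14 days before screening up to first dose (baseline visit for standard of care) and stopped before that date. This classifies all 91, 210 and 378 pairs above.
- Define concomitant as any medicine taken on or after that date through the reference end date in SAP Appendix 2, including medicines stopped on the day of first dose.
- Tabulate medicines first started after the reference end date separately as follow-up medications.
- Remove or redefine the combined label in the listing.

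Reconcile both protocol 5.3.4 and 8.1 to this single definition. Aligning 8.1 with 5.3.4 alone would not do, because early-screening medicines would stay unclassified when screening runs beyond 14 days. Check the amendment 4 wording first.

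The cost is minor rewording and one extra table. The data are already collected through Week 28.

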14. DIAGNOSTIC, SURGICAL, OR THERAPEUTIC PROCEDURES DURING THE STUDY

The diagnostic, surgical, or therapeutic procedures during the study are recorded in the eCRF and will only be presented in a listing.

15. STUDY DRUG COMPLIANCE

Study drug administration diary data will be used to measure study drug compliance. Only diary entries with “Yes” in response to the question “Was the study drug administered per instructions today?” will be deemed compliant.

Subjects will be considered compliant overall for study drug administration if the calculated compliance is > 80%. Overall treatment compliance will be presented for percent compliance calculations using descriptive statistics and the number and percentage of subjects who are > 80% compliant by treatment group for the ITT and PP and SAF Analysis Sets.

15.1. DERIVATIONS

Compliance with double-blind study drug will be calculated as the number of doses administered divided by the planned number of doses expressed as a percentage. This can be summarized as:

$$\text{Overall percent compliance} = (\text{Total number of diary days marked “Yes” for study drug administration} / \text{Number of days on treatment}) * 100$$

where number of days on treatment will be calculated as (Date of last study drug – Date of first study drug + 1) and dose interruption days will not be excluded.

Drug administration diary data, first dose date, and last dose data are reported in the eCRF.

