5.3.3 Compliance with Dosing Regimens

Subject compliance with study drug dosing will be monitored by the sponsor/designee by counting and examining used and unused vials. In addition, compliance will be checked by site personnel at every visit by asking the subject or the subject's parent or guardian if they have administered the study drug according to instructions. If any doses have been missed, the reason for missed dose should be documented in the subject's source documentation including, as applicable, the eCRF.

Compliance is considered to be achieved if the subject has 80% of the planned doses administered.

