8.4 Other Variables

Other variables will be analyzed by treatment group including:

- Subject disposition
- Duration of study drug exposure
- Subjects will be considered compliant if study drug was taken according to protocol and assigned treatment group for $\geq 80\%$ of doses. Data will be taken from the Study Drug Accountability completed by the site staff. The number and percentage of subjects who were compliant will be presented by treatment group.
- The number and percentage of subjects who complete the study, are lost to follow up, or discontinued from the study (including reason for study withdrawal) will be summarized by treatment group.
- The study drug dose by duration will be summarized by treatment group.

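### SAP 15.1 describes compliance over planned doses but computes it over days on treatment, and a blank diary day scores as a missed dose

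*SAP*

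**What the plan says.** SAP 15 takes compliance from the diary: "Study drug administration diary data will be used to measure study drug compliance". A day counts only if the diary question on administration as instructed is answered 'Yes'. The classification rule is "Subjects will be considered compliant overall for study drug administration if the calculated compliance is > 80" per cent. Results are summarised for the ITT, per-protocol (PP) and safety sets.

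SAP 15.1 first gives a definition in words, "the number of doses administered divided by the planned number of doses expressed as a percentage". The formula that follows puts diary 'Yes' days over days on treatment, "where number of days on treatment will be calculated as (Date of last study drug – Date of first study drug + 1", and adds that "dose interruption days will not be excluded". That denominator is the same quantity as the extent of exposure in SAP 18.1. No rule is given for a drug-administration diary day left blank.

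SAP 6.4 lists non-compliance under Section 15 among the situations that may affect inclusion in the PP set.

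The supplied protocol says in 5.3.3: "Compliance is considered to be achieved if the subject has 80% of the planned doses administered". Its section 8.4 sets the threshold at 80% or more of doses and names another source: "Data will be taken from the Study Drug Accountability completed by the site staff".

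**The concern.** Two things can go wrong.

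- **Denominator.** The words point to the planned course, while the formula uses only the span the child was actually treated. Anyone reading the table against its stated definition would take a high percentage to mean that most of the 24-week course was given. For early stoppers the formula does not show that.
- **Blank days.** A blank day stays in the denominator and cannot enter the numerator, so missing information is scored as a missed dose. The SAP handles gaps differently for the PN/IV diary in 17.1.1: it averages over the recorded days and sets the value to missing when more than two days in a week are absent. The drug diary has no equivalent rule.

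The first affects how the compliance tables are read. The second can also affect who is in the PP set, which supports a sensitivity analysis of the primary efficacy variable (SAP 17.1.3).

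**Working it through.** The documents report no compliance figure to reproduce, so the check applies the two definitions to the same child.

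**Inputs.** Dosing is once daily for 24 weeks (protocol 5.3 and 5.3.1), which gives 24 × 7 = 168 planned doses. Neither document states this number. The first dose falls at the baseline visit (Day 0), and the Week 24 visit is on Day 168 with the antibody sample drawn before the last dose (Table 6-2), so 169 is also possible. I use 168 and check 169.

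**Early stopping.** Assume every diary day up to the last dose is 'Yes'.

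- SAP formula: 100 × 'Yes' days / (last dose date − first dose date + 1)
- Definition in words: 100 × doses / 168

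| Last dose on treatment day | SAP formula | Over 168 planned doses |
|---|---|---|
| 14 | 100% | 8.3% |
| 28 | 100% | 16.7% |
| 84 | 100% | 50.0% |
| 134 | 100% | 79.8% |
| 135 | 100% | 80.4% |

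Over 169 planned doses, the 28-day case is 28/169 = 16.6%.

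**Blank diary days.** Take a completer with 168 days on treatment and all doses given.

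- 33 blanks: 135/168 = 80.4%, compliant.
- 34 blanks: 134/168 = 79.8%, non-compliant.
- Vial accountability in both cases: 168/168 = 100%.

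With 169 days the boundary is the same: 33 blanks give 136/169 = 80.5% and 34 give 135/169 = 79.9%.

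**Reach.** SAP 6.4 limits PP to children who complete the treatment period, so the early stopper is outside PP whatever the score. The completer with blanks could be excluded. The supplied protocol (4.1) plans at least 10 children per arm, so one exclusion removes up to a tenth of an arm. As an illustration only, assume 6 responders of 10 (60%). Removing one responder gives 5/9 = 55.6%, and removing one non-responder gives 6/9 = 66.7%.

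**Cut-off.** At 168 days, 0.8 × 168 = 134.4, so 'more than 80%' and 'at least 80%' both need 135 'Yes' days. The two rules differ only when days on treatment is a multiple of 5, and then by one dose: 133 against 132 at 165 days, and 137 against 136 at 170 days.

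**The case against.** The strongest defence is that the formula is explicit and programmable. With once-daily dosing, days from first to last dose are the doses due while on treatment, and interruptions are kept in. This separates adherence from discontinuation, which is a legitimate aim. Early stopping is visible elsewhere, in the exposure categories (SAP 18) and disposition (SAP 10). A fixed 168 has its own faults: it can exceed 100% if 169 doses are given, and it labels a fully adherent child who is withdrawn as non-compliant. All of this stands. It argues for keeping the formula, but not for keeping words that describe a different quantity.

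On blanks, counting only 'Yes' is a stated, conservative choice. The diary question also captures whether the dose was given as instructed, which a used vial does not show. Diaries are checked for completeness at each visit (protocol 6.1.13), and nothing in the documents suggests that 34 unresolved blanks is likely. That limits the expected effect, but a rule for blanks is still missing.

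A reader might infer more than the documents support:

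- **That the SAP changed source and cut-off while declaring no change in 4.3.** The SAP is based on protocol amendment 4, and the supplied protocol's history ends at amendment 2. The mismatch is with the supplied version only. The supplied protocol also records dosing in the diary (7.1).
- **That children with diary gaps are automatically dropped from PP.** SAP 6.4 says such situations *may* affect inclusion, and SAP 6 settles membership at blinded data review.
- **That early stoppers enter PP, or always score 100%.** They are outside PP, and any missed or blank day before stopping lowers the score.

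**Conclusion.** The point holds in a limited form. Within SAP 15.1 the words and the formula do not match on a plain reading, whichever protocol version applies. The formula measures compliance while on treatment and can give 100% where the share of the planned course is 16.7%. The gap affects the ITT and safety compliance tables, not PP.

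Separately, scoring blanks as missed doses can class a fully dosed completer as non-compliant from 34 blanks onward and may cost that child a place in PP. The ITT efficacy results are unaffected, and the study does no hypothesis testing, so the importance is low.

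This rests on 168 planned doses (169 changes nothing material) and on taking planned doses to mean the full course. Reading them as doses planned while on treatment would reconcile words and formula, but the SAP does not say so. Whether source and cut-off depart from the governing protocol is undetermined without amendment 4, and the cut-off difference is nil at 168 days.

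**What to change.** 1. In SAP 15.1, label the existing measure as compliance while on treatment and correct the sentence above the formula to match.
2. Add one row to the compliance table: doses administered over doses planned to the Week 24 visit. State the planned count explicitly.
3. Add a rule for blank diary days: resolve them from the study drug accountability data, which SAP 18 already lists, before classifying a child as non-compliant for PP.
4. Check the source (diary or accountability) and the cut-off (more than 80% or at least 80%) against protocol amendment 4, and record any departure in SAP 4.3.

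The cost is some SAP wording, one table row and a little more derivation work. Early stoppers will show a lower planned-dose percentage, which is the information now missing from the table.
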